5.3. Medical History

General medical history (ie, conditions not specific to the disease being studied) data will be collected at screening and listed only. General medical history data will not be coded. A by-subject listing of disease-specific medical history will be provided by subject ID number (in ascending order) and medical history of abnormalities (in chronological order).

6. EFFICACY ANALYSES

6.1. Primary Efficacy Endpoint

6.1.1. Definition of the Primary Efficacy Endpoint

The primary efficacy endpoint is SVR12 defined as HCV RNA < LLOQ (ie, < 15 IU/mL) 12 weeks after cessation of treatment in the FAS. The COBAS[®] AmpliPrep/COBAS[®] TaqMan[®] HCV Quantitative Test v2.0 will be used to measure HCV RNA.

6.1.2. Primary Analysis of the Primary Efficacy Endpoint

No inferential statistics will be provided for efficacy endpoints. No statistical comparison will be conducted.

The point estimate of SVR12 rate and 2-sided 95% exact confidence interval (CI) based on Clopper-Pearson method will be provided {[Clopper 1934](#)} for the FAS.

6.1.3. Subgroup Analysis of the Primary Efficacy Endpoint

The point estimate of SVR12 rate and 2-sided 95% exact confidence interval (CI) based on Clopper-Pearson method will be provided {[Clopper 1934](#)} for the FAS, and also for each subgroup specified in Section 3.4.

A Forest plot will graphically present estimates and 95% confidence intervals of SVR12 rates for each subgroup.

6.2. Secondary Efficacy Endpoints

6.2.1. Definition of Secondary Efficacy Endpoints

Secondary efficacy endpoints include the following:

- The percentage of subjects who attain SVR at 4 weeks after stopping therapy, defined as HCV RNA < LLOQ (ie, < 15 IU/mL) 4 weeks after stopping treatment (SVR 4)
- The percentage of subjects with HCV RNA below LLOQ on treatment
- HCV RNA (\log_{10} IU/mL) and change from baseline in HCV RNA (\log_{10} IU/mL) through end of treatment (EOT)

- The percentage of subjects with virologic failure as the following:

On-treatment virologic failure

- HCV RNA \geq LLOQ after having previously had HCV RNA $<$ LLOQ, while on treatment, confirmed with 2 consecutive values (note, second confirmation value can be posttreatment), or last available on-treatment measurement with no subsequent follow-up values (ie, breakthrough)
- $> 1 \log_{10}$ IU/mL increase in HCV RNA from nadir while on treatment, confirmed with 2 consecutive values (note, second confirmation value can be posttreatment), or last available on-treatment measurement with no subsequent follow-up values (ie, rebound)
- HCV RNA persistently \geq LLOQ through 8 weeks of treatment (ie nonresponse)

Relapse

- HCV RNA \geq LLOQ during the posttreatment period having achieved HCV RNA $<$ LLOQ at end of treatment, confirmed with 2 consecutive values or last available posttreatment measurement
- Characterization of HCV drug resistance substitutions at baseline, during, and after therapy with SOF/VEL/VOX

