2. OBJECTIVES

The primary objective of this study is:

- To determine the efficacy of treatment with SOF/VEL/VOX FDC for 12 weeks as measured by the proportion of subjects with sustained viral response 12 weeks after cessation of treatment (SVR12)
- To evaluate the safety and tolerability of treatment with SOF/VEL/VOX FDC

The secondary objectives of this study are:

- To determine the proportion of subjects who attain SVR at 4 weeks after cessation of treatment (SVR4)
- To evaluate the proportion of subjects with virologic failure
- To evaluate the kinetics of circulating HCV RNA during treatment and after cessation of treatment
- To evaluate the emergence of viral resistance to SOF, VEL, and VOX during treatment and after cessation of treatment

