- 19) Clinically-relevant alcohol or drug abuse within 12 months of Screening. A positive drug screen will exclude subjects unless it can be explained by a prescribed medication; the diagnosis and prescription must be approved by the investigator
- 20) Use of any prohibited concomitant medications as described in Section 5.5
- 21) Known hypersensitivity to the study drug, the metabolites, or formulation excipient

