6.7.8. Viral RNA Sequencing / Phenotyping Sample

Plasma samples will be collected at Day 1 and each visit thereafter and may be archived for viral sequence analysis. At any unscheduled visit initiated for the purpose of confirming virologic breakthrough, a viral sequence analysis plasma sample must be collected.

Details regarding the collection, processing, and shipping of samples will be included in the lab manual.

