6.2.2. Analysis Methods for Secondary Efficacy Endpoints

For analyses of HCV RNA $<$ LLOQ by visit while on treatment and during the posttreatment (SVR) follow-up period, subjects will be assigned a value at each visit based on the analysis visit windows specified in Section 3.8.2. Missing values will be imputed based on the categorical imputation rules described in Section 3.6.1. The 2-sided 95% exact confidence interval based on Clopper-Pearson method will be provided for the percentage of subjects with HCV RNA $<$ LLOQ at each visit for FAS. The overall category for “HCV RNA $<$ LLOQ” will be split into the following 2 subcategories: “ $<$ LLOQ TND” for subjects with target not detected and “ $<$ LLOQ detected” for subjects with $<$ LLOQ detected in tabular displays.

Graphs for the percentage of subjects with HCV RNA $<$ LLOQ over time during treatment will be displayed.

Summary statistics will be presented for absolute values and change from baseline in HCV RNA (\log_{10} IU/mL) by visit through EOT. Imputation rules described in Section 3.6.1 will be used to assign HCV RNA values for missing values at a visit that are bracketed by “ $<$ LLOQ TND” and/or “ $<$ LLOQ detected”. Otherwise, a missing = excluded analysis will be performed. Plots of the mean \pm SD and median (Q1, Q3) of absolute values and changes from baseline in HCV RNA through EOT will be presented.

For the SVR12 endpoint analysis, a summary table of the number and percentage of subjects with SVR12, virologic failure (VF), and Other will be created. All subjects who achieve SVR12 will be categorized as SVR12. Virologic failure will be descriptively summarized as “on-treatment virologic failure” and relapse (which will be broken down by study drug completed yes/no). Subjects who do not achieve SVR12 and do not meet criteria for VF will be categorized as Other. The denominator for relapse will be the number of subjects who had HCV RNA < LLOQ on their last observed on-treatment HCV RNA measurement; otherwise, the denominator will be the number of subjects in the FAS.

In addition, a summary table of the number and percentage of subjects with HCV RNA < LLOQ and \geq LLOQ at the posttreatment follow-up visit (observed and imputed, with reasons for imputed) will be provided for each posttreatment follow-up visit. 95% Clopper-Pearson exact CIs will be presented for the overall proportion of subjects with HCV RNA < LLOQ.

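### The SAP relapse rule has no same-strain condition, so an HCV reinfection that meets it would be reported as relapse and virologic failure

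*SAP*

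**What the plan says.** SAP 6.2.1 defines relapse by HCV RNA level and timing: at or above LLOQ after treatment in a subject who was below "LLOQ at end of treatment, confirmed with 2 consecutive values or last available posttreatment measurement". Viral strain and genotype play no part.

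SAP 6.2.2 sorts the FAS into SVR12, virologic failure (on-treatment failure or relapse) and a residual class: "Subjects who do not achieve SVR12 and do not meet criteria for VF will be categorized as Other". On the relapse percentage it adds: "The denominator for relapse will be the number of subjects who had HCV RNA < LLOQ on their last observed on-treatment HCV RNA measurement".

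Resistance is a secondary objective in Protocol section 2: "To evaluate the emergence of viral resistance to SOF, VEL, and VOX during treatment and after cessation of treatment". SAP 6.2.1 lists the matching endpoint, "Characterization of HCV drug resistance substitutions at baseline, during, and after therapy with SOF/VEL/VOX", but the visible text of SAP 6.2.2 gives no method for it.

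On samples, Protocol 6.7.8 states: "Plasma samples will be collected at Day 1 and each visit thereafter and may be archived for viral sequence analysis". Appendix 2 marks sequencing plasma at Day 1 and at every later visit, including posttreatment Weeks 4 and 12, and describes its use as possible rather than committed. HCV genotyping is marked at Screening only. Neither document mentions HCV reinfection in its visible text.

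**The concern.** Clearing one HCV infection does not protect against another. A subject whose Day 1 virus was eradicated, and who acquires a different strain before the posttreatment Week 12 sample, has not failed SOF/VEL/VOX. If the RNA condition is met, however, the plan leaves only one label for this subject, relapse, and with it virologic failure.

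The proportion with virologic failure is a secondary objective. The protocol's rationale for retreatment (section 1.3.1) rests partly on treatment-emergent resistance being rare, and section 1.4 names multiclass resistance as the risk if treatment fails. In a study of about 50 subjects with few failures expected, a single mislabelled case would be a visible share of what is reported on both questions.

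**Working it through.** The documents state no figure to reproduce here: there is no hypothesis test, no power calculation and no reinfection rate. The check is a reading of the rules, followed by arithmetic for scale.

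**1. Path of one subject through the rules.** Suppose HCV RNA is below LLOQ at end of treatment and at posttreatment Week 4, and at or above LLOQ at posttreatment Week 12 with a new strain.
- SVR12 (SAP 6.1.1) needs RNA below LLOQ at Week 12, so it is not achieved.
- Relapse (SAP 6.2.1) is met. The Week 12 value is the last available one, so it counts without confirmation.
- *Other* (SAP 6.2.2) is closed, because a virologic failure criterion is met.

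The result is relapse, whatever the strain. By contrast, an isolated positive at Week 4 followed by a negative at Week 12 is not relapse.

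**2. Effect of one case.** Inputs: n = 50 (SAP 1.3), and all 50 assumed suppressed at the last on-treatment measurement, so that the relapse denominator is also 50. Exact limits are Clopper-Pearson, from beta quantiles: lower = B(0.025; x, n − x + 1), upper = B(0.975; x + 1, n − x). SAP 6.2.2 plans number and percentage for virologic failure, so these intervals are for scale only.

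| Subjects with posttreatment viremia | Relapse as written | Relapse with reinfection separated | SVR12, either way |
|---|---|---|---|
| 1 reinfection | 1/50 = 2.0% (0.05 to 10.65) | 0/50 = 0% (0 to 7.11) | 49/50 = 98.0% (89.35 to 99.95) |
| 1 reinfection and 1 true relapse | 2/50 = 4.0% (0.49 to 13.71) | 1/50 = 2.0% (0.05 to 10.65) | 48/50 = 96.0% (86.29 to 99.51) |

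For comparison, the POLARIS-1 SVR12 rate of 96.2% (Protocol 1.2.2.4.1.1) would give 50 × (1 − 0.962) = 1.9 subjects without SVR12. That counts every reason for non-response, and the protocol does not give the split.

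**3. How likely is a case?** The rate is an assumption: r = 1 to 10 per 100 person-years. With p = 1 − exp(−(r/100) × d/365.25), the expected number is 50p, and the chance of at least one case is 1 − (1 − p)^50.
- d = 84 days: 50p = 0.115 to 1.137; chance 10.9% to 68.3%.
- d = 146 days, the end of the FU-12 window in SAP Table 3-2: 50p = 0.199 to 1.959; chance 18.1% to 86.4%.

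The second line is an outer bound. The protocol's last visit is posttreatment Week 12 ± 5 days, so only late or unscheduled samples fall near day 146, although SAP 3.8.3 does select the latest HCV RNA record in the window. Nothing in the documents anchors the range of r.

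**The case against.** **Little depends on it.** SVR12 is unchanged and nothing is tested. An RNA-only rule is objective and, if anything, counts against the drug. With one or two failures, each case is visible in the listings and could be explained in the clinical study report. All of this stands and limits the weight of the point. It does not correct the table, which would still call a reinfection a relapse.

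**The event is rare and its rate is stipulated.** This also stands. Criterion 19 excludes clinically relevant drug abuse within 12 months of Screening and adds: "A positive drug screen will exclude subjects unless it can be explained by a prescribed medication". A reader might infer from the prescription exception, or from drug use that ended earlier, that the trial enrols a high-risk group. The documents do not say how many such subjects would enter, and the criterion on balance lowers the risk.

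**The resistance effect is conjecture.** A reader might infer that the plan would report a new strain's substitutions as treatment-emergent resistance. The visible SAP neither defines treatment-emergent resistance nor plans such a table, so this is a possible consequence and not a stated rule.

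**Reclassification invites favourable relabelling.** In an open-label, single-arm study run by the sponsor this is a fair warning. It is met by a criterion fixed in advance, by a default of relapse when sequence data are missing, and by showing both counts.

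**Redaction.** SAP 6.3 and 6.4 and Protocol 8.5.3 are blacked out and may touch on this. That cannot be checked; the visible definitions leave no route.

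**Conclusion.** The point holds as a gap in a definition. Followed as written, SAP 6.2.1 and 6.2.2 would report a reinfection that meets the RNA rule as relapse and virologic failure, and no same-strain check protects the resistance characterization.

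The size is 2.0 percentage points of relapse per case at n = 50, assuming all subjects are suppressed at end of treatment. The most likely number of cases is zero toward the low end of the assumed rates, which is the more plausible end given criterion 19.

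Two further readings should be avoided. A reader might infer that every posttreatment value at or above LLOQ is counted as relapse; the rule requires two consecutive values or the last available one. A reader might also infer that the primary result is at risk; SVR12 depends only on HCV RNA and is the same with or without the change. This is a low-priority refinement that is worth making because it is cheap.

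**What to change.** Before database finalization, state the following in SAP 6.2.1 and 6.2.2:

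- For every subject who meets the relapse definition, the Day 1 and failure samples will be sequenced and compared, by genotype and subtype first and then by a phylogenetic criterion set in advance.
- If the failure virus is a distinct strain, the subject remains a non-responder for SVR12, is shown as *Other (reinfection)* instead of relapse, and is flagged separately in the resistance characterization.
- If either sequence is missing or fails, the subject stays classified as relapse.
- The relapse and virologic failure counts are reported with and without the reclassification.

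The cost is SAP wording, one table row and the sequencing of a few samples. The plasma is already scheduled, and Protocol 6.6 requires a sequencing sample at unscheduled visits made to confirm virologic failure. Sequencing of these samples does become a commitment, where Protocol 6.7.8 leaves it optional; it also serves the stated resistance objective. The other downside is that the relapse count comes to depend partly on a sequence comparison, which is why both counts should be shown.

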6.2.2. Analysis Methods for Secondary Efficacy Endpoints

For analyses of HCV RNA $<$ LLOQ by visit while on treatment and during the posttreatment (SVR) follow-up period, subjects will be assigned a value at each visit based on the analysis visit windows specified in Section 3.8.2. Missing values will be imputed based on the categorical imputation rules described in Section 3.6.1. The 2-sided 95% exact confidence interval based on Clopper-Pearson method will be provided for the percentage of subjects with HCV RNA $<$ LLOQ at each visit for FAS. The overall category for “HCV RNA $<$ LLOQ” will be split into the following 2 subcategories: “ $<$ LLOQ TND” for subjects with target not detected and “ $<$ LLOQ detected” for subjects with $<$ LLOQ detected in tabular displays.

Graphs for the percentage of subjects with HCV RNA $<$ LLOQ over time during treatment will be displayed.

Summary statistics will be presented for absolute values and change from baseline in HCV RNA (\log_{10} IU/mL) by visit through EOT. Imputation rules described in Section 3.6.1 will be used to assign HCV RNA values for missing values at a visit that are bracketed by “ $<$ LLOQ TND” and/or “ $<$ LLOQ detected”. Otherwise, a missing = excluded analysis will be performed. Plots of the mean \pm SD and median (Q1, Q3) of absolute values and changes from baseline in HCV RNA through EOT will be presented.

For the SVR12 endpoint analysis, a summary table of the number and percentage of subjects with SVR12, virologic failure (VF), and Other will be created. All subjects who achieve SVR12 will be categorized as SVR12. Virologic failure will be descriptively summarized as “on-treatment virologic failure” and relapse (which will be broken down by study drug completed yes/no). Subjects who do not achieve SVR12 and do not meet criteria for VF will be categorized as Other. The denominator for relapse will be the number of subjects who had HCV RNA < LLOQ on their last observed on-treatment HCV RNA measurement; otherwise, the denominator will be the number of subjects in the FAS.

In addition, a summary table of the number and percentage of subjects with HCV RNA < LLOQ and \geq LLOQ at the posttreatment follow-up visit (observed and imputed, with reasons for imputed) will be provided for each posttreatment follow-up visit. 95% Clopper-Pearson exact CIs will be presented for the overall proportion of subjects with HCV RNA < LLOQ.

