3.4. Discontinuation Criteria

If a subject discontinues study dosing (for example, as a result of an AE, every attempt should be made to keep the subject in the study and continue to perform the required study-related follow-up procedures (see Section 6.5). If this is not possible or acceptable to the subject or investigator, the subject may be withdrawn from the study.

When medically feasible, the medical monitor must be consulted prior to subject discontinuation.

Study drug must be discontinued in the following instances:

- Intercurrent illness that would, in the judgment of the investigator, affect assessments of clinical status to a significant degree. Following resolution of intercurrent illness, the subject may resume study dosing at the discretion of the investigator
- Unacceptable toxicity or toxicity that, in the judgment of the investigator, compromises the ability to continue study-specific procedures or is considered to not be in the subject's best interest
- Virologic failure (as defined in Section 3.5)
- Pregnancy of female subject (refer to Appendix 4)
- Significant protocol violation that impacts subject safety
- Subject request to discontinue for any reason; it is important to determine whether the withdrawal of consent is primarily due to an AE, lack of efficacy, or other reason

- Subject noncompliance
- Discontinuation of the study at the request of Gilead, regulatory agency or an Institutional Review Board (IRB)/Independent Ethics Committee (IEC)

All subjects who terminate early will complete the ET visit and posttreatment Week 4 and 12 visits.

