1.1. Study Objectives

The primary objectives of this study are as follows:

- To determine the efficacy of treatment with sofosbuvir (SOF)/velpatasvir (VEL)/voxilaprevir (VOX) fixed dose combination (FDC) for 12 weeks as measured by the proportion of subjects with sustained viral response 12 weeks after cessation of treatment (SVR12)
- To evaluate the safety and tolerability of treatment with SOF/VEL/VOX FDC

The secondary objectives of this study are as follows:

- To determine the proportion of subjects who attain SVR at 4 weeks after cessation of treatment (SVR4)
- To evaluate the proportion of subjects with virologic failure
- To evaluate the kinetics of circulating HCV RNA during treatment and after cessation of treatment
- To evaluate the emergence of viral resistance to SOF, VEL, and VOX during treatment and after cessation of treatment

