3.6. Missing Data and Outliers

3.6.1. Missing Data

In general, missing data will not be imputed unless methods for handling missing data are specified.

For missing last dose date of study drug, imputation rules are described in Section 3.8.1. The handling of missing or incomplete dates for AE onset is described in Section 7.1.5.2, and for prior and concomitant medications in Section 7.4.

For analyses of categorical HCV RNA data, missing posttreatment HCV RNA data will have the missing data imputed. Missing on-treatment HCV RNA will have the missing data imputed up to the time of the last dose (for on-treatment displays). If the study day associated with the last dosing date is greater than or equal to the lower bound of a visit window, and the value at the visit is missing, the value will be imputed. If the study day associated with the last dosing date is less than the lower bound of a visit window then the on-treatment value at that visit will remain missing.

If a data point is missing and is preceded and followed in time by values that are “< LLOQ target not detected (TND)”, then the missing data point will be set to “< LLOQ TND”. If a data point is missing and preceded and followed by values that are “< LLOQ detected”, or preceded by “< LLOQ detected” and followed by “< LLOQ TND”, or preceded by “< LLOQ TND” and followed by “< LLOQ detected”, then the missing value will be set to “< LLOQ detected”. In these situations the data point will be termed a bracketed success; otherwise, the data point will be termed a bracketed failure (ie, \geq LLOQ detected). If a data point is missing and is not bracketed, the missing data point will also be termed a failure (ie, \geq LLOQ detected).

For the analyses of continuous HCV RNA efficacy data, when and only when a missing HCV RNA value is imputed as < LLOQ TND or < LLOQ detected according to the imputation rule described above, the corresponding continuous value will be imputed to LLOQ – 1 IU/mL. No other imputation will be performed for continuous HCV RNA data.

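### SAP 6.2.1 and 6.2.2: after an unconfirmed quantifiable last on-treatment HCV RNA value, a subject suppressed at posttreatment Week 4 and viraemic at Week 12 is filed as 'Other', not virologic failure

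*SAP*

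**What the plan says.** SAP 1.1 lists as a secondary objective "To evaluate the proportion of subjects with virologic failure". SAP 6.2.1 recognises four kinds of failure:

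- **Breakthrough:** HCV RNA ≥ LLOQ on treatment after an earlier value < LLOQ. It must be confirmed by two consecutive values (the second may be posttreatment), "or last available on-treatment measurement with no subsequent follow-up values (ie, breakthrough").
- **Rebound:** a rise of more than 1 log10 from the on-treatment nadir, with the same confirmation rule, "or last available on-treatment measurement with no subsequent follow-up values (ie, rebound").
- **Nonresponse:** HCV RNA persistently at or above "LLOQ through 8 weeks of treatment (ie nonresponse").
- **Relapse:** HCV RNA ≥ LLOQ posttreatment in a subject who was below "LLOQ at end of treatment, confirmed with 2 consecutive values or last available posttreatment measurement".

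SAP 6.2.2 then tabulates SVR12, VF and a remainder: "Subjects who do not achieve SVR12 and do not meet criteria for VF will be categorized as Other". The relapse denominator is limited to subjects whose last observed on-treatment value was < LLOQ. The other rows use the full analysis set (FAS).

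Subjects with missing outcomes can reach the same remainder. For SVR12, SAP 3.6.1 says: "If a data point is missing and is not bracketed, the missing data point will also be termed a failure". A subject lost to follow-up after a suppressed end of treatment fails SVR12, meets no VF criterion and becomes 'Other'.

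SAP 6.2.2 also plans a separate table of HCV RNA < LLOQ and ≥ LLOQ at each posttreatment visit, split into observed and imputed values.

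**The concern.** The four criteria do not cover every observed viraemic outcome. Relapse depends on a single value, the one at end of treatment. If that value is quantifiable, the subject cannot relapse by definition, even when the next sample is < LLOQ and HCV RNA later returns. Breakthrough does not catch the subject either, because the next sample fails to confirm it. A subject who was suppressed after treatment and viraemic at posttreatment Week 12 is then reported as not a virologic failure.

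The stake is the VF proportion and the content of the 'Other' row, which would combine a measured treatment failure with subjects who have no outcome data. With about 50 subjects and few failures expected, one subject is visible in the result.

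**Working it through.** The plan has no figure to reproduce. It states no VF rate, the sample size is the number of eligible prior failures, and no hypothesis is tested.

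**Step 1. Apply each criterion to the sequence.** The sequence is: Week 8 < LLOQ, Week 12 ≥ LLOQ, posttreatment Week 4 < LLOQ, posttreatment Week 12 ≥ LLOQ. End of treatment is read as the last observed on-treatment value, which is how 6.2.2 defines the relapse denominator.

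| Criterion | Met? | Reason |
|---|---|---|
| Breakthrough | No | Week 12 is not confirmed by the next value, and follow-up values exist |
| Rebound | No | Same reason, even if the Week 12 rise exceeds 1 log10 |
| Nonresponse | No | Week 8 was < LLOQ |
| Relapse | No | End-of-treatment value was ≥ LLOQ |
| SVR12 | No | Posttreatment Week 12 is ≥ LLOQ |

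The result is 'Other'.

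**Step 2. Check how general this is.** Fix posttreatment Week 12 as observed ≥ LLOQ, let each of Weeks 2, 4, 8, 12 and posttreatment Week 4 be < or ≥ LLOQ, and assume no confirmed rebound. For completers there are 2^5 = 32 patterns.

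- If Week 12 is < LLOQ, the subject is a relapse (some also meet an on-treatment criterion).
- If Weeks 8 and 12 are both ≥ LLOQ, the subject is a breakthrough (any earlier value < LLOQ) or a nonresponder (none).
- If Week 8 is < LLOQ, and Week 12 and posttreatment Week 4 are both ≥ LLOQ, breakthrough is confirmed.
- What remains is Week 8 < LLOQ, Week 12 ≥ LLOQ, posttreatment Week 4 < LLOQ, with Weeks 2 and 4 free: 2 × 2 = 4 of 32 patterns.

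The same route exists for 2 of 16 patterns when treatment stops after Week 8, and 1 of 8 when it stops after Week 4. These are counts of combinations, not probabilities.

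**Step 3. Size if one such subject occurs.** With the FAS at 50, 1/50 = 2.0 percentage points. Clopper-Pearson 95% intervals:

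| VF count | Proportion | 95% CI |
|---|---|---|
| 0/50 | 0% | 0 to 7.11% |
| 1/50 | 2.0% | 0.05 to 10.65% |
| 2/50 | 4.0% | 0.49 to 13.71% |

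**Step 4. Likely frequency.** The documents give no rate for this sequence. A ceiling comes from all SVR12 failures of any kind, using the SOF/VEL/VOX results in Protocol 1.2.2.4.1:

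- POLARIS-1: (100 − 96.2)% × 50 = 1.9 subjects
- POLARIS-4: (100 − 97.3)% × 50 = 1.35 subjects

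To expect even one subject with this sequence, it would have to make up 1/1.9 = 53% to 1/1.35 = 74% of all SVR12 failures. That is implausible, so well under one subject is expected. Both rates come from populations that differ from this one.

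**Step 5. Test the remedy.** If relapse may also follow a value < LLOQ at an earlier posttreatment visit, all 4 completer patterns become relapse, as do the 2 and the 1 found for earlier stops. With posttreatment Week 4 observed, the only viraemic patterns left in 'Other' are subjects who stop before Week 8, were never < LLOQ on treatment, and are ≥ LLOQ at both posttreatment visits. The change also takes in an early stopper first seen < LLOQ at posttreatment Week 4 and then viraemic.

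**The case against.** **The information is not lost.** The observed/imputed table in SAP 6.2.2 gives the number of subjects with measured HCV RNA ≥ LLOQ at posttreatment Week 12. SAP 4.1 counts subjects with no posttreatment Week 4 or Week 12 assessment, and Protocol 8.3 provides an HCV RNA listing. With about 50 subjects, anyone in 'Other' can be traced. This stands. It does not change the VF proportion itself, and no planned table crosses 'Other' with observed viraemia.

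**A true late breakthrough would normally be confirmed.** Protocol 3.5 calls for confirmation within 2 weeks, and SAP 6.2.1 accepts a posttreatment confirming value. This stands as a reason for rarity. If the repeat is < LLOQ and taken more than 3 days after the last dose, however, SAP 3.8.2 treats it as posttreatment and the subject still cannot relapse. Two of the four completer patterns also lack the two consecutive values < LLOQ just before Week 12 that Protocol 3.5 requires for its first criterion.

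**Stronger readings the documents do not support.**

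- A reader might infer that the VF proportion is understated as a matter of course. It is lower only if such a subject occurs. Ordinary relapse, confirmed breakthrough and nonresponse through Week 8 are all counted.
- A reader might also count as missed failures those who stop before Week 8 without ever reaching < LLOQ. They do fall in 'Other' unless they rebound, and their outcome can be observed, since Protocol 3.4 says: "All subjects who terminate early will complete the ET visit and posttreatment Week 4 and 12 visits". But they have not had the 8 weeks of treatment that nonresponse requires, so keeping them outside VF is a defensible definition. They are also few: early stops of any kind were 5/415 and 2/333 in POLARIS-1 and POLARIS-4 (all arms), which scale to 0.60 and 0.30 in 50.

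**Conclusion.** The point holds, and it is minor. As written, a subject with earlier suppression, an unconfirmed last on-treatment value ≥ LLOQ, a value < LLOQ at posttreatment Week 4 and a value ≥ LLOQ at posttreatment Week 12 is classed as 'Other', solely because of that one unconfirmed value. Each such subject lowers the VF proportion by 2 percentage points at n = 50. The subject is an SVR12 failure either way, so the primary endpoint does not move.

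This rests on three assumptions: end of treatment means the last observed on-treatment value; no confirmed rebound occurred earlier; and any additional sample leaves the classification unchanged. The rarity is a judgement bounded by the POLARIS failure rates, not an estimate from the documents.

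**What to change.** 1. In SAP 6.2.1, define relapse as posttreatment HCV RNA ≥ LLOQ after HCV RNA < LLOQ at end of treatment or at any earlier posttreatment visit, with the same confirmation or last-available rule. State that a subject who already meets an on-treatment failure criterion is counted there only, because the wider definition can overlap with it.
2. In SAP 6.2.2, define the relapse denominator as all subjects with HCV RNA < LLOQ at the last on-treatment measurement or at any posttreatment visit. Adding only those who relapse would let the outcome decide who is in the denominator.
3. Optionally, split 'Other' into observed posttreatment HCV RNA ≥ LLOQ with VF criteria not met (for example, unsuppressed subjects who stop before Week 8 without rebound) and no observed posttreatment HCV RNA ≥ LLOQ. This is a reporting step and leaves the VF rate unchanged.

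The cost is a few sentences in the SAP and, with the optional step, one more table row. No new data are needed. The reported VF rate could become slightly less favourable.
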